#### **14.6 Secondary Efficacy analyses**

Stratified analysis for the primary endpoint will be performed using the ANCOVA model adjusted for gender and age group. Subjects will be classified to one of the following strata:

1. Male, aged 18-40 years
2. Male, aged >40 years
3. Female, aged 18-40 years
4. Female, aged >40 years

The changes of the following response outcomes from baseline to week 3 will be summarized by descriptive statistics:

- Blood Tests: LDL-C, HDL-C, total cholesterol, TAG, creatinine and fasting glucose.
- Cardiometabolic risk factors: Blood pressure, body temperature, weight, BMI, waist and hip circumferences.
- Musculoskeletal-related traits: Handgrip strength, peak expiratory flow rate, bio-impedance, gait speed and body balance

The secondary efficacy analyses will be performed on the ITT population only.

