### 3 PROTOCOL SYNOPSIS

**Title:** The Effect of Soya Beverage Fortified with Plant Sterol on Major Serum Lipids in Normocholesterolemic, Healthy Southern Chinese Individuals

**Phase:** Phase II

**Study Site:** Queen Mary Hospital, The University of Hong Kong

**Study Design:** This is a local, single-center, two-arm, randomized, double-blind, placebo-controlled study that examine the effect of the consumption of a soya beverage enriched with plant sterol for 3 weeks. Subject will be randomly assigned to receive either the investigational or control product. The randomization will be stratified by both gender (male and female) and age group (18-40 years and >40 years).

Blood specimens will be collected at the baseline and at the end of the consumption period, which will be subjected to laboratory analysis.

**Study Objectives:** **Primary Objective:** To examine the effect of the consumption of a plant sterols fortified soya beverage on serum LDL cholesterol in healthy, free-living normocholesterolemic individuals

**Secondary Objective:** To examine health-benefits by consuming the plant sterols fortified soya beverage in terms of serum total triglyceride, total and HDL cholesterol, other cardiometabolic risk factors and musculoskeletal-related traits.

**Study Population:** Two hundred (200) Southern Chinese male or female in Hong Kong who aged 18 or above with good general health will be recruited in this study.

**Investigational and Control Product Administration:** The investigational product is a soya drink fortified with 2g plant sterols per pack and the control product is the same soya drink except without plant sterols.

Subjects will be asked to consume 1 pack of either investigational or control product daily for 3 consecutive weeks, each pack consumed once with main meal. Subjects consuming test product will therefore consume 2 g of plant sterols daily.

**Study Duration:** This study is estimated to last for 12 months (from subject enrollment until completion of data analyses)

**Subject Participation Duration:** 3 weeks

**Estimated Time to Complete Enrollment:** 9 months

**Study Endpoints:** **The primary endpoint** is the mean serum LDL-C at the end of week 3 after the consumption of plant sterols fortified soya beverage or control product.

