#### Lipid-Modifying Effect of Plant Sterols

The cholesterol lowering effect of plant sterols were demonstrated more than 50 years ago (13). Earlier studies demonstrated that pure plant sterol supplementation lowered both total serum cholesterol and LDL-C in individuals with hypercholesterolemia (14). A number of clinical trials have been examined the efficacy of plant sterols/stanols as a cholesterol lowering agent when incorporated into low fat foods including yoghurt, bread and cereal (15). Results from several epidemiological studies consistently reported that dietary incorporation of plant sterols/stanols (1.5-2 g/day) reduces serum LDL-C levels 5% to 15% with minimal adverse events (16-18). In addition, the impact of the consumption of plant sterols/stanols-enriched foods is relatively consistent in both normolipidemic and dyslipidemic individuals including those treated with lipid-lowering agents, regardless of background diet and that there is little or no effect on high-density lipoprotein (HDL) cholesterol or triglyceride (TAG) levels (19-20). It has now been recognized by the United States Federal Drug Administration (US FDA) and the American Heart Association that dietary incorporation of plant sterols is recommended for blood cholesterol reduction and thereby reducing the risk of CVD (21-22).

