## 7 OBJECTIVES

### 7.1 Study Objectives

- **The primary objective** of this study is to assess the efficacy of daily consumption of 2g plant sterols as provided by one pack of 250 ml soya beverage product each taken during the main meal for 3 consecutive weeks, in lowering the blood LDL-C level among Southern Chinese.
- **The secondary objective** is to examine if there is other health-benefits by consuming the plant sterols-enriched soya beverage, such as glucose and TAG lowering effect.

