### **14.4 Demographics and Baseline Characteristics**

Demographics data and other baseline characteristics including medical history, dietary information, physical examination and prior medication will be summarized by appropriate descriptive statistics.

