#### **14.5 Primary Efficacy analysis**

ANCOVA will be carried out to compare the serum LDL-C level at week 3 between the groups. The baseline of the response outcome will be used as a covariate to control for initial group differences. A log transformation will be performed if the normality assumption for the ANCOVA model is violated. And if the normality assumption is still not sustained, non-parametric approach might be performed.

The primary efficacy analysis will be performed on both the ITT and the PP populations.

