#### **14.8 Compliance of the study products**

The compliance of the study products will be summarized by descriptive statistics per study group.

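### The secondary objective on triglycerides, total and HDL cholesterol and glucose has no planned between-arm estimate or confidence interval

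*Combined protocol and SAP*

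**What the plan says.** The secondary objective is worded in two places. The synopsis (section 3) has: "To examine health-benefits by consuming the plant sterols fortified soya beverage in terms of serum total triglyceride, total and HDL cholesterol", and goes on to cardiometabolic and musculoskeletal measures as classes. Section 7.1 says the secondary objective "is to examine if there is other health-benefits by consuming the plant sterols-enriched soya beverage, such as glucose and TAG lowering effect". Together they name four outcomes: TAG, total cholesterol, HDL-C and glucose. Section 13.1.2 makes the changes from baseline in these and the other measures the secondary endpoints.

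For analysis, 14.6 and the synopsis use the same sentence: "The changes of the following response outcomes from baseline to week 3 will be summarized by descriptive statistics". It gives no model, contrast, interval or test, and does not mention study group.

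Two between-arm models are planned, both for LDL-C. Section 14.5 states: "ANCOVA will be carried out to compare the serum LDL-C level at week 3 between the groups". Section 14.6 adds: "Stratified analysis for the primary endpoint will be performed using the ANCOVA model adjusted for gender and age group".

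**The concern.** Both arms drink the same soya beverage every day; only the sterols differ. A change within one arm therefore mixes any sterol effect with regression to the mean, diet change during the study and the effect of adding a daily soya drink. Only the difference between the arms isolates the sterols, and that is what an objective about benefit of the fortified product needs.

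The background in 6.1.2 also expects of sterols that "there is little or no effect on high-density lipoprotein (HDL) cholesterol or triglyceride (TAG) levels", while 7.1 asks about TAG lowering. A small or null effect is best reported as a difference with an interval that shows which effects the data exclude. A table of changes does not show that directly.

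If no contrast is fixed in advance, the choice of model, and of which outcomes to feature, falls after unblinding. Section 18 allows the product supplier to use the results for marketing, which is a further reason to settle that choice beforehand.

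**Working it through.** **1. Count of outcomes (list in 14.6).** Blood tests 6, cardiometabolic 6 (blood pressure counted once, waist and hip separately) and musculoskeletal 5, so 6 + 6 + 5 = 17. LDL-C is covered by the ANCOVA in 14.5, leaving 16. Four are named in the objective (TAG, total cholesterol, HDL-C, glucose), leaving 12 others.

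**2. Search for a contrast elsewhere.** Sections 14.5 and 14.6 model LDL-C only. Section 14.4 covers baseline data; 14.7 to 14.9 cover adverse events, compliance and concomitant medication. None gives a between-arm estimate for the 16.

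**3. The plan's own sample size (14.1).** Inputs: SD 0.85 mmol/l, correlation 0.7, difference 0.28 mmol/l, power 0.8, alpha 0.05 (taken as two-sided).
- Residual SD = 0.85 × √(1 − 0.7²) = 0.607.
- Normal approximation: 2 × (1.960 + 0.842)² × 0.607² / 0.28² ≈ 73.8, so 74 per group.
- With the noncentral t distribution and one covariate, power is 0.796 at 74 and 0.801 at 75, so 75 per group.
- 150 / (1 − 0.25) = 200.

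The stated figures are reproduced. The trial is sized for LDL-C alone, with 75 evaluable subjects per arm.

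**4. Precision of a between-arm estimate.** The documents give no SD or correlation for the secondary outcomes, so half-widths of the 95% CI are in SD units and the correlation ρ is assumed. Further assumptions: 75 per arm, equal SD at both visits, and no further variance explained by gender and age group.
- ANCOVA (treatment, own baseline, gender, age group; 145 df): t(0.975, 145) × √[(1 − ρ²) × 2/75].
- Unadjusted difference in change (148 df): t(0.975, 148) × √[2(1 − ρ) × 2/75].

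| ρ | ANCOVA | Difference in change | Ratio |
|---|---|---|---|
| 0.5 | 0.280 | 0.323 | 0.866 |
| 0.7 | 0.230 | 0.250 | 0.922 |
| 0.9 | 0.141 | 0.144 | 0.975 |

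ANCOVA is thus about 13%, 8% and 3% narrower. With 100 per arm and ρ = 0.7 the half-widths are 0.199 and 0.216.

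**5. Multiplicity, if each outcome were tested at 0.05.** Under independence, 1 − 0.95⁴ = 0.185 for the four named outcomes and 1 − 0.95¹⁶ = 0.560 for all 16. The second figure is illustrative only, because the outcomes are related. Height is measured at baseline only, for example, so each subject's BMI change is the weight change divided by a constant.

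**The case against.** The strongest reply is that this is a deliberate design choice. The trial states one hypothesis (6.2), powers one outcome (14.1) and plans inference on one endpoint (14.5). Describing the rest without formal inference is a recognised way to avoid unadjusted testing. This stands in large part for outcomes such as creatinine, body temperature or peak flow, where a model is close to preference. It is weaker for the four outcomes that the objective names, since 14.6 presents these as efficacy analyses and the objective asks about an effect.

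A second reply is that by-arm tables let a reader subtract the means. That is so if n, mean and SD are shown by arm, and the loss of precision would be small. But the layout is not stated, and such a difference would be neither baseline-adjusted nor pre-specified.

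A reader might infer from the missing reference to group that the arms will be pooled. The documents do not support that. Section 14.4 is equally silent ("physical examination and prior medication will be summarized by appropriate descriptive statistics"), while 14.8 is explicit ("The compliance of the study products will be summarized by descriptive statistics per study group"). The wording is uneven, and silence does not establish pooling.

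A reader might also want models required for all 16 outcomes. That goes too far. The schedule in section 5 and its remarks name only bio-impedance among the musculoskeletal measures, so it is not clear there that handgrip strength, peak flow, gait speed and body balance are taken at both visits.

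**Conclusion.** The gap is real and worth closing, though it is not critical. A stated objective has no planned comparative answer: four named outcomes lack a between-arm estimate and CI, as do 12 others for which the case is weaker. The count and the absence of any other contrast come straight from the text.

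The precision argument is secondary. It rests on an assumed correlation (the plan's 0.7 is for LDL-C only), and the half-widths cannot be put into clinical units. The main value is a comparison specified before unblinding.

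The documents do not support reading this as a threat to the trial's main conclusion. The LDL-C analysis, the error rate and the sample size are unaffected, and the added estimates would remain exploratory.

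**What to change.** Amend 14.6 and the synopsis along these lines:

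> Changes are tabulated by study group (n, mean, SD, or median and IQR if skewed). For total cholesterol, HDL-C, TAG and fasting glucose, the between-arm difference with its 95% CI is estimated by ANCOVA with treatment, the outcome's own baseline, gender and age group. On the untransformed scale this equals the baseline-adjusted difference in change. The log-transformation and non-parametric fallback of 14.5 apply; log-scale results are reported as ratios. The same model may be applied to the other listed continuous outcomes that are measured at both visits. All these estimates are exploratory and support no confirmatory efficacy claim.

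Gender and age group are included because randomisation is stratified by them and 14.6 already adjusts for them in its LDL-C model. The fallback matters for an outcome such as TAG if it proves skewed. Section 14.5 does not name the non-parametric method, so the text should say which estimate any such interval belongs to.

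The cost is a paragraph of wording and four model fits, or more if the option is used. The downside is more intervals to interpret and a multiplicity risk of about 0.19 for four independent tests. The exploratory label discloses that risk but does not remove it. Before modelling the musculoskeletal measures, confirm that they are collected at both visits. Bio-impedance will have fewer subjects, because those with metal implants are excluded from it. The primary analysis and sample size need no change.

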#### **14.7 Safety Analysis**

The incidence of AE such as nausea, abdominal cramps, vomiting, diarrhea, and flatulence will be summarized by frequency tables per treatment group. Data listings will be reported.

#### **14.8 Compliance of the study products**

The compliance of the study products will be summarized by descriptive statistics per study group.

#### **14.9 Concomitant Medications**

Data listing of concomitant medications will be reported per study group.

#### **14.10 Interim Analyses**

No interim analyses will be planned for this study.

## **15 SOURCE DOCUMENTS AND ACCESS TO SOURCE DATA/DOCUMENTS**

### **15.1 Source Documents**

The Investigators will maintain source documents for each subject in the study.

Source documents are defined as original documents, data and records. This may include hospital records, clinical and office charts, laboratory data/information, subjects' diaries or evaluation checklists, pharmacy dispensing and other records, recorded data from automated instruments, microfiches, photographic negatives, microfilm or magnetic media, and/or x-rays. The Investigator could create source data worksheets and document information that are not available on the hospital records.

Designated investigator staff will document all the information required by the protocol. It is the investigator's responsibilities to ensure the compliance of protocol and the completeness and accuracy of collected data. Investigator will only instruct qualified site personnel to make any required corrections or additions of collected data. All source documents should be completed in a neat, legible manner to ensure accurate interpretation of data.

The Investigator(s)/institution(s) will permit any trial-related monitoring, audit, IEC/IRB review, and regulatory inspection(s), providing direct access to source data documents.

## **16 DATA HANDLING AND RECORD KEEPING**

### **16.1 Data Management Responsibilities**

Data management will be carried out by data management personnel at CTC, HKU. A data management plan (DMP) will be developed to outline all works related to data management activities, including but not limited to Electronic-Case report forms (eCRF) design, data collection, data cleaning and data storage.

However, data collection and accurate documentation are the responsibility of the study staff under the supervision of the principal investigator. All source documents and laboratory reports must be reviewed by the study team and data entry staff, who will ensure that they are accurate and complete. Unanticipated problems and adverse events must be reviewed by the investigator or designee.

### **16.2 Data Capture Methods**

An Electronic Data Capture (EDC) system will be setup by CTC, HKU. eCRFs will be developed and to collect information for this study. All information on the eCRFs must also be reflected in the subject source documents. The principal investigator will review the eCRFs for completeness and accuracy of eCRFs.

Data entered by the site personnel on the web-based EDC system will be submitted and stored securely in the study database. The data management personnel could access and review the study database for completeness and logical consistency. A comprehensive validation check program is built in the system for identifying missing data, out-of-range data and other data inconsistencies. The data management personnel will also perform regular validation check to generate discrepancy reports and individual data query to investigators for solution of data.

Once all the study data are cleaned, the data manager will lock the study database. Once the database is locked, the randomization codes will be unblinded and the data is made available for data analyses.

### **16.3 Study Records Retention**

Study documents should be retained for a minimum of 25 years after the end of the study. No records will be destroyed without the written consent of the sponsor-investigator, if applicable.

The study database will be retained in CTC, HKU for retrieval for at least three years from the date of the clinical study report is submitted to sponsor-investigator.

## **17 ETHICS/PROTECTION OF HUMAN SUBJECTS**

### **17.1 Ethical Standard**

The investigator will ensure that this study is conducted in full conformity with the principles set forth in The Belmont Report: Ethical Principles and Guidelines for the Protection of Human Subjects of Research, as drafted by the US National Commission for the Protection of Human Subjects of Biomedical and Behavioral Research (April 18, 1979) and codified in 45 CFR Part 46 and/or the ICH E6.

### **17.2 Institutional Review Board**

The protocol, informed consent form(s), recruitment materials, and all subject materials will be submitted to the IRB for review and approval. Approval of both the protocol and the consent form must be obtained before any subject is enrolled. Any amendment to the protocol will require review and approval by the IRB before the changes are implemented in the study.

### **17.3 Informed Consent Process**

Informed consent is a process that is initiated prior to the individual agreeing to participate in the study and continues throughout study participation. Extensive discussion of risks and possible benefits of study participation will be provided to subjects and their families, if applicable. A consent form describing in detail the study procedures and risks will be given to the subject. Consent forms will be IRB-approved, and the subject is required to read and review the document or have the document read to him or her. The investigator or designee will explain the research study to the subject and answer any questions that may arise. The subject will sign the informed consent document prior to any study-related assessments or procedures. Subjects will be given the opportunity to discuss the study with their surrogates or think about it prior to agreeing to participate. They may withdraw consent at any time throughout the course of the study. A copy of the signed informed consent document will be given to subjects for their records. The rights and welfare of the subjects will be protected by emphasizing to them that the quality of their clinical care will not be adversely affected if they decline to participate in this study.

The consent process will be documented in the clinical or research record.

#### **17.4 Subject Confidentiality**

Subject confidentiality is strictly held in trust by the sponsor-investigator, study staff, and their agents. This confidentiality is extended to cover testing of biological samples and genetic tests in addition to any study information relating to subjects.

The study protocol, documentation, data, and all other information generated will be held in strict confidence. No information concerning the study or the data will be released to any unauthorized third party without prior written approval of the sponsor-investigator.

The study monitor or other authorized representatives of the sponsor-investigator may inspect all study documents and records required to be maintained by the investigator, including but not limited to, medical records (office, clinic, or hospital) for the study subjects. The clinical study site will permit access to such records.

#### **17.5 Future Use of Stored Specimens and Other Identifiable Data**

Subjects can choose freely if they agree to the future use of his/her specimens for any genetic or cell analysis related to risk factors of cardiometabolic disease in the future. Residual specimens and personal data will be maintained for at least 25 years after the study is completed only under subject's consent. All data collected and written assignment for this study will be stored in a secured server. The server will then be locked in a cabinet in a locked room. Only principal investigator ([name] [name]) and his delegates will have access to this locked cabinet. Confidentiality will be protected as all specimens will be coded and anonymized. All data will be destroyed after the storage period.

## **18 PUBLICATION/DATA SHARING POLICY**

The clinical trials registration policy will be adopted for this study. Before the start of the study, registration will be done in an acceptable public trials registry such as *ClinicalTrials.gov*.

Vitasoy International Holdings Ltd. and the University of Hong Kong are the legal co-owners of the data. Vitasoy International Holdings Ltd. is free to use the data and/or any results derived from the data or publications based on that data for marketing purposes, scientific purposes, internal or educational uses.

Publications describing study results must be submitted to Vitasoy International Holdings Ltd at least 30 days before planned manuscript submission and at least 14 days prior to planned abstract submission. If the Vitasoy International Holdings Ltd has no objection to publication requests within the review-period, the submission for publication will proceed.

